### Non-Binding Futility Stopping Rule

Based on futility characteristics simulations, the futility stopping rule is developed, which is based on the conditional power for the non-inferiority of the composite endpoint of tBPAR or eGFR (MDRD4) < 50 ml/min/1.73m^2. Recommendation to stop the trial due to futility can be considered if the calculated conditional power is  $\leq 2\%$  based on the scenario described in [Section 2.12.1](#).

### 2.12.2 Other Analyses

In addition to the futility analysis described in the previous section, the following analyses will be performed for the **6-month completers with data up to Month 6**.

#### Demographic and background information:

- Summary of demographics and transplant background information by treatment

**Disposition:**

- Summary table and listing of patient disposition at Month 6: ongoing study/study treatment, completed study/study treatment, and premature discontinuations of study/study treatment with reasons by treatment
- Summary of patient disposition at Month 6 by treatment and **randomization strata** (CNI: CsA vs TAC, and donor type: living vs standard criteria vs expanded criteria deceased donor)
- KM plot of premature discontinuation of study medication

**Study medication:**

- Summaries of average daily doses of study drug (everolimus and MPA) as well as CNI (cyclosporine and tacrolimus)
- Summaries of number (percent) of patients with EVR/CNI trough levels within/below/above target ranges
- Box-plots of EVR/CNI trough levels with target ranges displayed

**Efficacy (up to Month 6):**

- Summary of raw incidence rate (n and %) for the following events by treatment as well as by treatment and randomization strata
  - composite of treated biopsy proven acute rejection (tBPAR) or  $GFR < 50 \text{ mL/min/1.73m}^2$
  - composite of tBPAR, graft loss, death or  $GFR < 50 \text{ mL/min/1.73m}^2$
  - $GFR < 50 \text{ mL/min/1.73m}^2$
- Summary of Kaplan-Meier incidence rate for the following events by treatment as well as by treatment and **randomization strata**:
  - composite of tBPAR, graft loss or death
  - composite of graft loss or death
  - individual endpoints of death, graft loss, tBPAR, BPAR, tAR, AR
- Kaplan-Meier plot for:
  - Composite endpoint of tBPAR, graft loss or death
  - tBPAR
  - Graft loss/death
- Forest plot of efficacy events

Exceptions for Month 6 incidence rate: For those patients who were beyond Month 6 in the study, tBPAR up to Month 12 and eGFR (MDRD4) at Month 12 will be used instead if they are available at the time of the futility analysis.

**Renal function:**

- Summaries of estimated GFR (MDRD4) and serum creatinine by visit, as well as by visit and randomization strata

- Summaries of the changes from Week 4 for estimated GFR (MDRD4) and serum creatinine by visit
- Plot of mean and 95% CI for estimated GFR (MDRD4) by visit
- Incidence of patients with estimated GFR(MDRD4) in specified categories (<30; 30-<45; 45-<60; 60-<90; >90 ; <50 mL/min/1.73m^2) by visit (Week 4 and onward visits)

#### AE/SAE

Summary by primary SOC & PT for the followings:

- Frequent events ( $\geq 10\%$  in any treatment group) regardless of study drug relationship
- Serious events regardless of study drug relationship by primary SOC & PT, and additionally by **randomization strata**
- Infections regardless of study drug relationship by type of infection & specific micro-organism
- Events suspected to be related to study drug
- Events leading to study drug discontinuation by primary SOC & PT, and additionally by **randomization strata**
- Primary cause of death/graft loss

Note: infections should be included as part of AEs.

#### Laboratory

- Summary of lipids (total cholesterol and triglycerides) by visit
- Summary of Hematology (haemoglobin, platelets and total WBC) by visit

The transplant background information, efficacy and GFR analyses will also be performed for the full analysis set with all data available at the time of the futility analysis (e.g. including data prior to Month 6 for patients recently enrolled or data beyond Month 6 for patients who have been in the study over 6 months). AEs/infections leading to study drug discontinuation and SAEs/serious infections will be analyzed for the safety analysis set with all data available at the time of the futility analysis.

Listings for efficacy events and GFR will be provided for the full analysis set, and listings for everolimus and CNI trough levels and AEs will be provided for the safety analysis set.

### 2.12.3 Calculation of Prediction Interval and Conditional Power

#### 2.12.3.1 Predicted Event and Event Rate

Let  $N$  be planned sample size per treatment group ( $N=1020$ ),  $n_i$  be the number of patients for the futility analysis (6-month completers) for the treatment group  $i$  (e.g.  $i$  for EVR and MPA),  $x_i$  be the observed events in the  $n_i$  patients in the treatment  $i$ , and  $p_{f,i}$  is assumed event rate in the future patients in the treatment  $i$ , the predicted (expected) events for the treatment  $i$  will be calculated as follows:

$$e_i = x_i + (N - n_i)p_{f,i}$$

The predicted event rate for the treatment  $i$  will be

$$p_i = e_i/N$$

### 2.12.3.2 Prediction Interval

Predicted difference in event rate between the two groups will be

$$p_{EVR} - p_{MPA} = e_{EVR}/N - e_{MPA}/N$$

Prediction interval for the difference will be (Evans, Li and Wei, 2007)

$$(p_{EVR} - p_{MPA}) \pm Z_{0.975} SE_{full}$$

$$\text{where } SE_{full} = \text{SQRT}[p_{EVR}(1 - p_{EVR})/N + p_{MPA}(1 - p_{MPA})/N]$$

### 2.12.3.3 Conditional Power

The predicted difference of  $p_{EVR} - p_{MPA}$  approximately follows a Normal distribution, test statistic  $Z$  can be constructed as

$$Z = (p_{EVR} - p_{MPA} - \delta) / SE_{full}$$

where  $\delta$  is margin ( $\delta = 0.10$  corresponding to  $H_{01}$  and  $H_{03}$  for non-inferiority analyses, and  $\delta = 0$  corresponding to  $H_{03}$  for superiority analysis).

Assuming  $y_i$  be number of events to be obtained in the future patients in the treatment  $i$ , let

$\bar{x}_i = \frac{x_i}{n_i}$  and  $\bar{y}_i = \frac{y_i}{N - n_i}$  be observed event rate in the  $n_i$  patients for the futility analysis and

estimated event rate in the future patients respectively in the treatment  $i$ , the  $Z$  constructed above can be decomposed to

$$\begin{aligned} Z &= (p_{EVR} - p_{MPA} - \delta) / SE_{full} \\ &= \left[ \frac{n_{EVR} \bar{x}_{EVR} + (N - n_{EVR}) \bar{y}_{EVR}}{N} - \frac{n_{MPA} \bar{x}_{MPA} + (N - n_{MPA}) \bar{y}_{MPA}}{N} - \delta \right] / SE_{full} \\ &= \left[ \frac{n_{EVR} (\bar{x}_{EVR} - p_{f,EVR}) + (N - n_{EVR}) (\bar{y}_{EVR} - p_{f,EVR})}{N} - \frac{n_{MPA} (\bar{x}_{MPA} - p_{f,MPA}) + (N - n_{MPA}) (\bar{y}_{MPA} - p_{f,MPA})}{N} + (p_{f,EVR} - p_{f,MPA}) - \delta \right] / SE_{full} \\ &= \left\{ \frac{(N - n_{EVR}) (\bar{y}_{EVR} - p_{f,EVR})}{N} - \frac{(N - n_{MPA}) (\bar{y}_{MPA} - p_{f,MPA})}{N} + \left[ \frac{n_{EVR} (\bar{x}_{EVR} - p_{f,EVR})}{N} - \frac{n_{MPA} (\bar{x}_{MPA} - p_{f,MPA})}{N} \right] + (p_{f,EVR} - p_{f,MPA}) - \delta \right\} / SE_{full} \end{aligned}$$

To reject the null hypothesis,  $Z$  should be  $< -Z_{0.975}$ , namely

$$\frac{(N - n_{EVR}) (\bar{y}_{EVR} - p_{f,EVR})}{N} - \frac{(N - n_{MPA}) (\bar{y}_{MPA} - p_{f,MPA})}{N} < -Z_{0.975} SE_{full} + \delta - (p_{f,EVR} - p_{f,MPA}) - \left[ \frac{n_{EVR} (\bar{x}_{EVR} - p_{f,EVR})}{N} - \frac{n_{MPA} (\bar{x}_{MPA} - p_{f,MPA})}{N} \right]$$

$$\text{Let } A = -Z_{0.975} SE_{full} + \delta - (p_{f,EVR} - p_{f,MPA}) - \left[ \frac{n_{EVR} (\bar{x}_{EVR} - p_{f,EVR})}{N} - \frac{n_{MPA} (\bar{x}_{MPA} - p_{f,MPA})}{N} \right]$$

Then to reject the null hypothesis, we need

$$\frac{(N - n_{EVR}) (\bar{y}_{EVR} - p_{f,EVR})}{N} - \frac{(N - n_{MPA}) (\bar{y}_{MPA} - p_{f,MPA})}{N} < A$$

Therefore, conditional power will be calculated as follows

$$\Pr\left(\frac{(N-n_{EVR})(\overline{y}_{EVR}-p_{f,EVR})}{N}-\frac{(N-n_{MPA})(\overline{y}_{MPA}-p_{f,MPA})}{N}<A\right)$$

The variance of  $\frac{(N-n_{EVR})(\overline{y}_{EVR}-p_{f,EVR})}{N}$  is

$$\frac{p_{f,EVR}(1-p_{f,EVR})\left(\frac{N-n_{EVR}}{N}\right)^2}{N-n_{EVR}}=\frac{(N-n_{EVR})p_{f,EVR}(1-p_{f,EVR})}{N^2}=B_{EVR}$$

Similarly, the variance of  $\frac{(N-n_{MPA})(\overline{y}_{MPA}-p_{f,MPA})}{N}$  is

$$\frac{p_{f,MPA}(1-p_{f,MPA})\left(\frac{N-n_{MPA}}{N}\right)^2}{N-n_{MPA}}=\frac{(N-n_{MPA})p_{f,MPA}(1-p_{f,MPA})}{N^2}=B_{MPA}$$

The conditional power is

$$\begin{aligned} &\Pr\left(\frac{(N-n_{EVR})(\overline{y}_{EVR}-p_{f,EVR})}{N}-\frac{(N-n_{MPA})(\overline{y}_{MPA}-p_{f,MPA})}{N}<A\right) \\ &= \Pr\left(\frac{\frac{(N-n_{EVR})(\overline{y}_{EVR}-p_{f,EVR})}{N}-\frac{(N-n_{MPA})(\overline{y}_{MPA}-p_{f,MPA})}{N}}{\sqrt{B_{EVR}+B_{MPA}}}<\frac{A}{\sqrt{B_{EVR}+B_{MPA}}}\right) \\ &= \Phi\left(\frac{A}{\sqrt{B_{EVR}+B_{MPA}}}\right) \end{aligned}$$

This calculation is adapted from (Chow and Chang, 2007).

For this futility analysis, the predicted event rate and conditional power for the key secondary endpoint of tBPAR, graft loss or death will be calculated based on raw event rate rather than using KM method.

### 3 Determination of Sample Size

The sample size for this study was chosen with the goals to (1) have high power to evaluate non-inferiority in both the overall population *and* the TAC alone population and (2) have adequate power to evaluate superiority in the both the overall population *and* the TAC alone population.

With a sample size of n=1020 randomized per arm (EVR, MPA), the study has at least 95% power to demonstrate non-inferiority ( $\alpha=0.025$ , one-sided) in the overall and TAC alone populations at Month 12. There are at least 73% and 63% power ( $\alpha=0.025$ , one-sided) to demonstrate superiority of 7% or more in the overall and TAC alone populations, respectively.

The calculations are based on the following assumptions:

- 80% of patients are randomized to tacrolimus, 20% of patients are randomized to cyclosporine

- 20% and 30% patients are excluded from the PP population at Months 12 and 24 respectively
- For non-inferiority, the event rate in each arm is 50%, based on study results from RAD001A2309 and [Ekberg 2007](#), and the non-inferiority margin for the primary composite endpoint is 10%.
- For the evaluation of superiority, the event rate in the MPA + sCNI arm is 50%.

## 4 Appendix

### 4.1 Visit-Windows

*Visit-windows* will be used to summarize the data by visit and are defined in terms of weeks and months; these will be based on the study schedule of evaluation and comprised a set of days “around” the nominal visits. Visit-windows are non-overlapping; all together they cover the entire study period, e.g., the visit-window *Month 2* comprises study days 45 to 90, i.e., it has the nominal visit Month 2 as “center” and includes the 15 days preceding study day 60 and 30 days thereafter. Generally, visit-windows are not symmetrical around the nominal visit day.

As patients do not necessarily have their examinations at the exact scheduled time, it might be misleading if all data with the same nominal visit number are lumped together for a by-visit analysis. Thus, all data (including reported unscheduled assessments) are “re-aligned” according to the window schema given below. Note that the visit windows defined in the protocol are used to guide investigators whereas the ‘re-aligned’ visit windows in [Table 4-1](#) (simply called visit windows in the following) will be used for the analyses.

**Table 4-1 Visit Windows**

Re-aligned Visit	Visit window	Relative to randomization date		
		Start day of Visit window	Midpoint	End day of Visit window
1	Screening/Baseline	Inform Consent		randomization
2	Day 4	1 (post-randomization)	4	5
3	Week 1	6	7	10
4	Week 2	11	14	21
5	Week 4	22	28	44
6	Month 2	45	60	90
7	Month 4	91	120	150
8	Month 6	151	180	225
9	Month 9	226	270	315
10	Month 12	316	360	450
11	Month 18	451	540	630
12	Month 24	631	720	810

Re-aligned Visit	Visit window	Relative to randomization date		
		Start day of Visit window	Midpoint	End day of Visit window
13	Month 12 Treatment Endpoint (TEP)	1		450
14	Month 12 Study Endpoint (SEP)	1		450
15	Month 24 TEP	1		810
16	Month 24 SEP	1		810

## 4.2 Missing Data Handling

### 4.2.1 Missing GFR Data Imputation

#### 4.2.1.1 Main Imputation

The following is the main imputation method for handling missing eGFR data at Month 12. A similar imputation rule can be applied for missing eGFR at Month 24. These imputations will be applied to the primary analyses for the composite endpoint of tBPAR or eGFR < 50 mL/min/1.73m^2, as well as for eGFR alone. For the component of eGFR < 50 mL/min/1.73m^2, a value for missing eGFR as a continuous variable will be imputed first, then it will be dichotomized in order to derive this endpoint.

- Under the assumption of missing not at random (MNAR), patients who lost their grafts will be assigned a value of zero for their missing eGFR at the visits on and after graft loss;
- Multiple imputation: Otherwise, under the assumption of missing at random (MAR), patients who had missing values including those who died with a functioning graft will have a 12-month eGFR imputed using multiple imputation method based on the covariates/factors CNI, region, donor type, HLA mismatch ( $\leq 3$  vs  $> 3$ ), induction therapy, recipient gender, recipient age, donor age, and DGF, and all eGFR (MDRD4) data collected at the visit windows during the analysis period of interest. In the multiple imputation, recipient age, donor age and eGFR (MDRD4) data will be treated as continuous variables. To help preserve the relationship between outcome and covariates within each treatment, a separate model will be run for each treatment. This will also help ensure that the imputation model does not make stronger assumptions on data relations than the analysis model.

To ensure that results can be replicated, the data should be sorted by patient number before running the model (the data should be in horizontal format with one row per patient). If there are multiple renal function assessments within a visit window, guidelines given in [Section 2.1](#) will be followed, i.e., the closest value to the planned visit (midpoint of visit window for post-baseline visits) will be taken (if tie, the last will be used) for imputation. In addition, the seed used in the multiple imputation will be 2433.

See dummy SAS codes below.

```
proc mi data=DATAIN out=DATAOUT nimpute=100 seed=2433;
  by treatment;
  class CNI region donor HLA induction gender_r DGF;
```

```
fcs reg (/details);  
var CNI region donor HLA induction gender_r age_r age_d DGF GFR_vis1  
GFR_VIS2 ... GFR_VISm;  
run;
```

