6.4 Efficacy

Treated Biopsy Proven Acute Rejection (tBPAR)

A treated BPAR is any condition where the subject received anti-rejection treatment and was histologically diagnosed as acute rejection (according to the Banff 2009 criteria, Appendix 6). Renal biopsies will be collected for all cases of suspected acute rejection.

Kidney allograft biopsy

For all suspected rejection episodes, regardless of initiation of anti-rejection treatment, an allograft biopsy must be performed within 48 hrs. Biopsies will be read by the local pathologist according to the updated Banff 2009 criteria (Appendix 6). The results of the biopsy read by the local pathologist will be listed on the Kidney Allograft Biopsy CRF. The results will be used for subject management for acute rejection. The local pathologist will remain blinded to

treatment. Any biopsies performed according to local practice (e.g. not for cause) should also be recorded.

Graft Loss

The allograft will be presumed to be lost on the day the subject starts dialysis and is not able to subsequently be removed from dialysis. If the subject undergoes allograft nephrectomy prior to starting permanent dialysis, then the day of nephrectomy is the day of graft loss. The reason for graft loss will be recorded on the Graft Loss CRF. This will be reported on the M12 or M24 study completion CRF with Graft Loss as the reason for study discontinuation and on the appropriate Dosage Administration Record CRF(s) if death occurs while on randomized treatment. Graft loss is considered a Serious Adverse Event and should be reported on the Adverse Event CRF (as serious) and the SAE reported to the local Novartis Drug Safety and Epidemiology Department local Novartis Drug Safety and Epidemiology (DS&E) Department within 24 hr.

Death

In the event of subject death, the SAE leading to Death should be reported to Novartis DS&E within 24 hr. The events leading to the death should be entered on the Adverse Event CRF and the death should be indicated on the appropriate Dosage Administration Record CRF(s) (if death occurs while on randomized treatment) and on the Study Completion CRF.

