## **2.7 Analysis of Other Secondary Objective**

### **2.7.1 Other Secondary Endpoints**

Other secondary efficacy variables to be considered are as follows:

1. Composite endpoint of tBPAR or eGFR (MDRD4)  $< 50$  mL/min/1.73m^2 at Month 24
2. Composite endpoint of tBPAR excluding grade IA rejections or eGFR (MDRD4)  $< 50$  mL/min/1.73m^2 at Months 12 and 24
3. Composite efficacy failure of tBPAR, graft loss, or death at Month 24
4. Composite efficacy failure of tBPAR, graft loss, death, or loss to follow-up at Month 12 and 24
5. Components of composite efficacy failure as well as BPAR, AR, tAR at Month 12 and Month 24
  - a. AR
  - b. tAR
  - c. BPAR
  - d. tBPAR
  - e. tBPAR excluding grade IA rejections;
  - f. Humoral rejection
  - g. Graft loss
  - h. Death.
6. Composite endpoint of tBPAR, graft loss, death or eGFR  $< 50$  mL/min/1.73m^2 at Months 12 and 24
7. Composite endpoint of graft loss or death at Month 12 and Month 24
8. Composite endpoint of BPAR, graft loss or death at Month 12 and Month 24
9. eGFR (MDRD4)  $< 50$  mL/min/1.73m^2 at Month 12 and Month 24

10. Renal function (eGFR by MDRD4, CKD-EPI and Cystatin C-based formulae) at Month 12 and Month 24
11. Renal function change from Week 4 to Month 12 and Month 24
12. Evolution of renal function (eGFR by MDRD4) from Week 4 to Month 12 and Month 24 (slope analyses).

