### 2.7.3.2 eGFR by MDRD4

The eGFR by MDRD4 analyses will be based on FAS with multiple imputation used as the primary method for the handling of missing data. Renal function and change from Week 4 will be summarized by visit with descriptive statistics. A two-sided t-test will be performed to compare the two treatment groups at each visit. A plot of mean and 95% CI of eGFR (MDRD4) by visit will be provided. These will be repeated for on-treatment renal function analyses.

In addition, if different CNI effect is shown from the logistic regression, eGFR(MDRD4) and change in eGFR(MDRD4) from Week 4 by visit will be summarized for the subgroups of CNI (CsA and TAC).

The proportion of patients by eGFR(MDRD4) range (<30, 30-<45, 45-<60, ≥60 mL/min/1.73m^2) will be summarized by visit.

For eGFR(MDRD4) at Month 12 and Month 24, analysis of covariance (ANCOVA) will be performed with covariates/factors of treatment, CNI, region, interaction of treatment and CNI, interaction of treatment and region, donor type, HLA mismatch (≤3 vs >3), induction therapy, recipient gender, recipient age, donor age, DGF, and eGFR (MDRD4) at Month 1. In the model, recipient and donor age will be treated as continuous variables. The missing Month 12 or Month 24 values will be imputed using the primary multiple imputation method.

The evolution of renal function (eGFR by MDRD4) will be evaluated via a mixed effect model with intercept and study day as random effects and using covariates/factors treatment, study day, CNI, region, interaction of treatment and study day, interaction of treatment and CNI, interaction of treatment and region, donor type, HLA mismatch (≤3 vs >3), induction therapy, recipient gender, recipient age, donor age, DGF, and eGFR (MDRD4) at Month 1. In the model, study day, recipient and donor age, and eGFR (MDRD4) at Week 4 will be treated as continuous variables. Unstructured variance-covariance can be assumed, and the eGFR (MDRD4) data at Week 4 and onward will be used. The denominator degrees of freedom will be calculated using the Kenward-Roger method. No imputation will be applied for missing data. Based on the mixed effect model, the treatment groups will be compared, slope of renal function evolution for each treatment group will be assessed, and eGFR(MDRD4) value at Month 12/24 will be estimated.

See dummy SAS codes below.

```
proc mixed method=ml;
  class trt CNI region donor HLA induction gender_r DGF usubjid;
```

```

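### Read literally, the SAP zero rule scores a graft lost before Week 4 as no change from Week 4, the same as a stable graft

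*SAP*

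**What the plan says.** SAP 4.2.1.1 (main imputation) states that "patients who lost their grafts will be assigned a value of zero for their missing eGFR at the visits on and after graft loss". It covers the composite endpoint "as well as for eGFR alone", and adds that "A similar imputation rule can be applied for missing eGFR at Month 24". Other missing values are multiply imputed under missing at random.

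SAP 2.7.3.2 then says: "The eGFR by MDRD4 analyses will be based on FAS with multiple imputation used as the primary method for the handling of missing data". Under the same heading, "Renal function and change from Week 4 will be summarized by visit with descriptive statistics", and "A two-sided t-test will be performed to compare the two treatment groups at each visit". SAP 2.7.1 lists "Renal function change from Week 4 to Month 12 and Month 24" as other secondary endpoint 11, and Protocol 2.2 has the matching objective, worded as change from Month 1.

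Three other places bear on this:

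- Protocol 6.4 has graft loss entered on the study completion form with "Graft Loss as the reason for study discontinuation", so eGFR after the loss will usually be missing and take the zero.
- Protocol 9.4.3 assigns the zero to the 12-month value only. The wording about all visits on and after the loss is the SAP's.
- SAP 4.2.1.2 repeats the all-visits zero in the sensitivity imputation.

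Neither document excludes grafts lost before Week 4 from the change analysis or gives them a different score.

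**The concern.** Zero is a sensible score for the eGFR level at Month 12 or 24 once the graft has gone. In a change score it fails if it also fills the reference visit, because the two zeros cancel. The same event then gets very different scores depending only on whether it happened before or after Week 4. The earliest losses are scored better than any functioning graft that declines.

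What is at stake is a between-arm comparison of a listed secondary endpoint. If one arm has more graft losses before Week 4, the change analysis does not show it, and the error always favours that arm.

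**Working it through.** The plan gives no figure for change from Week 4, so there is none to reproduce. The check is direct subtraction under the stated rule, followed by a sizing on assumptions.

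**Inputs from the documents**
- Zero at missing visits on and after graft loss (SAP 4.2.1.1).
- Week 4 window Days 22 to 44, Month 12 window Days 316 to 450, Month 24 window Days 631 to 810 (SAP Table 4-1).
- 1020 patients per arm (Protocol 9.7).
- Nearby eGFR means: 57.2 at Month 6 and 56.3 at Month 12 in study A2309 (SAP 2.12.1); 57.1 (SD 19.5) and 51.7 (SD 20) at Month 12 in the ASSET study (Protocol 1.1).

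**Assumptions, not in the documents**
- Week 4 mean 50 mL/min/1.73m², range 40 to 60, equal in both arms.
- SD of change 15 to 20.
- Early graft-loss rates: results are shown per percentage point.

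**Step 1. Score per patient**, as eGFR at Month 12 or 24 minus eGFR at Week 4:

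| Patient | Week 4 | Month 12/24 | Change |
|---|---|---|---|
| Graft lost before Day 22, no later eGFR | 0 | 0 | 0 − 0 = 0 |
| Stable functioning graft | 50 | 50 | 50 − 50 = 0 |
| Graft lost after the Week 4 value | 50 | 0 | 0 − 50 = −50 |

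The first row needs no assumption. The last is −40 to −60 over the assumed range. Zero fills missing values only, so an eGFR observed in the Week 4 window before a loss within Days 22 to 44 is kept.

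**Step 2. Difference hidden between arms**, relative to scoring early losses like later ones: (difference in early-loss proportion) × (Week 4 mean).
- 1 point, mean 50: 0.01 × 50 = 0.50 mL/min/1.73m².
- 1 point, mean 40 to 60: 0.40 to 0.60.
- 1.5 points, mean 50: 0.015 × 50 = 0.75.
- Equal early loss in both arms: 0.

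**Step 3. Against the precision of the comparison**: SE = SD × √(2/1020).
- SD 15: 15 × 0.0443 = 0.66, so 0.50 is 0.75 SE.
- SD 20: 20 × 0.0443 = 0.89, so 0.50 is 0.56 SE.

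**Step 4. Where the double zero does and does not enter**
- Change from Week 4 by visit, with its t-tests (SAP 2.7.3.2): enters.
- ANCOVA at Months 12 and 24: adjusts for Month 1 eGFR. If the zero-filled value is the covariate, an early loss is 0 on both sides and part of the loss is adjusted away. The SAP does not say which value is used.
- Primary endpoint: not affected, since 0 at Month 12 is below 50 and counts as an event.
- Key secondary endpoint and Kaplan-Meier graft-loss endpoints: not affected; they use the event itself.
- Month 12/24 eGFR level: not affected; one zero, correctly carried.
- Slope model, and the CKD-EPI and Cystatin C analyses: no imputation, so no zero.

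**The case against.** The strongest reply concerns reach. SAP 4.2.1.1 introduces the method as one for missing eGFR at Month 12, Protocol 9.4.3 zeroes only the 12-month value, and the all-visits wording may simply prepare the visit variables for the imputation procedure. On that view the zero was never meant for the Week 4 reference. This may well be the intention, but the text does not say it: the rule names all visits on and after the loss, and the change analysis is told to use that imputation.

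A second reply is that 0 may be defensible, since a patient with no graft at Week 4 has no function left to lose, and other endpoints carry the early failure. That is a possible estimand, but the SAP does not state it, and a t-test on the full analysis set does not express it.

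A reader might go further and infer that the trial fails to penalise a regimen causing more early graft loss. The documents do not support that. Early loss counts in the primary endpoint, the key secondary endpoint, the graft-loss endpoints and the mean eGFR level, which is tested beside the change. Change from Week 4 is also outside the hierarchical testing procedure, so no confirmatory claim rests on it.

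A reader might also infer that early losses noticeably improve an arm's mean change. That needs a clearly negative mean change among the other patients. The only nearby drift in the documents is 56.3 − 57.2 = −0.9 from Month 6 to Month 12 in study A2309. Zeros in 1% to 2% of patients would then move the mean by only 0.009 to 0.018. Nor does the listing of renal graft thrombosis in SAP 2.8.3 show any imbalance between arms before Week 4; it shows only that the event is a recognised risk.

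**Conclusion.** The point holds as a defect in a stated rule for one secondary endpoint. On the literal SAP text, a graft lost before Day 22 with no later eGFR scores a change of exactly 0, while a loss after Week 4 scores minus the Week 4 value. The sensitivity imputation does not help, because it repeats the rule. The on-treatment repeat does not rescore these patients either: it uses data only up to two days after the last dose, so they would generally drop out of it.

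The exact zero follows from the text. The size does not: the Week 4 mean, the SD of change and the early-loss rates are all absent. On the assumptions above, about 0.5 mL/min/1.73m², or 0.56 to 0.75 SE, is hidden per percentage point of imbalance. Nothing is hidden if early loss is balanced and the Week 4 means are equal. That is enough to matter for reading this endpoint, and it gives no reason to doubt the primary or key secondary results. It should be corrected because the correction is cheap.

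**What to change.** State in SAP 4.2.1.1 that the zero applies at outcome visits only, in line with Protocol 9.4.3, and not to the Week 4 reference. For grafts lost before the Week 4 window, impute the Week 4 reference from baseline covariates and pre-loss eGFR only. The post-loss zeros must be left out of that imputation model: the main model uses every eGFR visit as a variable, so a patient's later zeros would pull the imputed Week 4 value down. State also which Month 1 value the ANCOVA uses for these patients.

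Report the number of such patients by arm. Show change from Week 4 among patients with a functioning graft at Week 4 as a labelled supplementary analysis, read alongside the zero-filled Month 12/24 level. It should not replace the main analysis: it conditions on a post-randomisation event and still gives early loss no penalty.

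The cost is a few SAP sentences and a small programming change. The downside is an imputed, counterfactual reference value for a few patients. If outputs already exist, the corrected analysis can be added as a labelled supplement.
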